4.3. PER PROTOCOL SET

The Per Protocol Set consists of all subjects who receive at least one dose of study treatment and who have a Week 18 (or ET) visit MRI-PDF assessment completed no more than 14 days following the final dose of study treatment. Subjects who have less than 80% treatment compliance will also be excluded from the Per Protocol Set.

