4.4 COMPLIANCE WITH INVESTIGATIONAL PRODUCT

At applicable clinic visits during the Double-Blind Treatment Period (see Section 5.1.3), subjects will be queried about their compliance with taking their assigned study drug as instructed. The number of full and empty study drug pouches will be captured on the electronic case report form (eCRF).

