3.3.4. Missing Data and Outliers

Every effort will be made to obtain required data at each scheduled evaluation from all subjects who have been treated. For subjects who do not complete the 18-week evaluation, endpoints that will only be measured at Week 18 or the Early Termination (ET) visit (i.e., LFC, HOMA-IR, Pro-C3, ELF) will have the value at the ET visit carried forward for the missing Week 18 visit.

For all non-LFC secondary endpoints measured at at least one post-baseline timepoint other than Week 18/ET, missing Week 18 values will be imputed using a multiple imputation procedure for all subjects with an available measurement prior to Week 18. Multiple imputation relies on the assumption that the data are missing at random. This method of imputation produces unbiased estimators of the mean and standard error, and, as such, is preferred over single imputation methods. For this method, the procedure requires production of multiple datasets containing plausible values for each missing value. These plausible values are generated using available auxiliary information (site, treatment, baseline assessment value, baseline LFC, and baseline ALT).

Using a set of values rather than a single value better accounts for the uncertainty about the value being imputed. For this imputation, the Markov chain method will be used. SAS PROC MI will be used to generate 10 possible imputed datasets.

For each variable that has imputations performed, the following steps will be followed:

1. Missing values will be imputed using PROC MI. This will result in 10 datasets per variable.
2. Efficacy endpoints will be derived from the appropriate set of 10 datasets produced by PROC MI using the imputed values.
3. Each efficacy endpoint will be analysed 10 times (once per source dataset) using the appropriate statistical model for that endpoint.
4. For each endpoint, the results from the analysis from each of the 10 datasets will be combined using PROC MIANALYZE to produce an inferential result for the parameter of interest.

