3.3.7. Definitions and Terminology

Age

The age of a subject is defined as the number of whole years between the subject's birth date and the treatment start date.

Day 0 (Baseline)

Day 0 is the earliest day that study drug is initiated.

Study Day

Study Day is defined relative to Baseline (Day 0). Thus, the study day of an event is calculated as:
$$\text{Study Day} = \text{event date} - \text{date of Day 0}.$$

Study Visit

Study Visit is the nominal visit as recorded on the CRF.

Days on Treatment

Days on Treatment is calculated as Final Day on Treatment based on the End of Study eCRF page – First Day on Study Treatment + 1.

Baseline Value

For purposes of analysis, the baseline value is defined as the last non-missing value obtained prior to initiation of study drug.

Change from Baseline

Change from baseline for a given endpoint is defined as the Study Day X value minus the Baseline Value.

Percent (Relative) Change from Baseline

Percent, or relative, change from Baseline for a given endpoint is defined as the change from Baseline at Study Day X divided by the Baseline value, multiplied by 100 $((\text{CFB}/\text{BASE}) \times 100)$.

Adverse Event

An AE is defined as any untoward medical occurrence associated with the use of a drug in humans, whether or not considered drug related. An AE can be any unfavorable and unintended sign (including an abnormal laboratory finding), symptom, or disease (new or exacerbated) temporally associated with the use of the investigational product, regardless of whether it is considered to be related to the investigational product. All AEs will be recorded on the Adverse Event CRF.

Treatment-emergent Adverse Event

A TEAE will be an AE that occurred during the study after the first dose of study drug or that was present prior to dosing and exacerbates after the first dose of study drug. Additionally, it is assumed that an Adverse Event which was reported to have started on Day 1 without an associated onset time occurred after the initiation of study drug.

Concomitant Medications

Concomitant medications are those medications taken on or after the initiation of study drug. This definition includes medications started prior to the initiation of study drug, but continuing concomitantly with study drug.

Prior Medications

Prior medications are those medications taken prior to the initiation of study drug.

Total Bile Acid

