4.1. EFFICACY SET

The Efficacy set will consist of all randomized subjects who complete at least 80 days of study drug dosing and have a Week 18 (or ET) visit MRI-PDFP assessment. Subjects in this set will be analyzed according to the treatment to which they were randomized. This set will be utilized for analyses of efficacy.

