5.1. SUBJECT DISPOSITION, DEMOGRAPHIC AND BASELINE CHARACTERISTICS

Subject disposition will be presented for all randomized subjects. For each treatment group the following will be presented: the number of subjects who meet all eligibility criteria, the number of

subjects included in the Safety, Efficacy and Modified Efficacy sets, the number of subjects who completed the study and discontinued from the study, and the reasons for early discontinuation at any point. Additionally, the number of subjects dosed will be presented and the number of days on study treatment will be summarized for all treated subjects.

Demographic data and baseline characteristics including age, gender, race, and ethnicity, weight at Baseline, height at Baseline, body mass index (BMI), Baseline LFC, Baseline cT1, Baseline alanine aminotransferase (ALT), Baseline aspartate aminotransferase (AST), Baseline ELF, and Baseline HbA1c will be summarized using descriptive statistics for the Safety population, and will be presented by treatment group. This information will be reviewed for baseline differences, but no statistical testing will be performed.

Data on drug accountability and total amount of study drug received will be summarized by treatment group. Total amount of study drug received will be calculated as the sum over the duration of the study of study drug dispensed – study drug returned. Study drug compliance will then be calculated as this amount divided by the expected amount of drug received based on the number of on-treatment days the subject was on the study x 100.

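### The SAP's Per Protocol Set has no minimum exposure, so it is looser on exposure than the Efficacy Set and cannot act as a stricter check on the primary result

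*SAP*

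**What the plan says.** - **Per Protocol Set (SAP 4.3).** A single dose is enough exposure for entry. The scan condition limits the set to subjects "who have a Week 18 (or ET) visit MRI-PDF assessment completed no more than 14 days following the final dose of study treatment". One further condition concerns adherence: "Subjects who have less than 80% treatment compliance will also be excluded from the Per Protocol Set". No minimum duration is given.
- **Compliance (SAP 5.1).** Drug dispensed minus drug returned, "divided by the expected amount of drug received based on the number of on-treatment days the subject was on the study", times 100.
- **Days on Treatment (SAP 3.3.7).** "Final Day on Treatment based on the End of Study eCRF page", minus the first day, plus 1. Gaps are not subtracted. SAP 5.1 does not refer to this definition.
- **Efficacy Set (SAP 4.1).** Subjects must "complete at least 80 days of study drug dosing" and have a Week 18 or ET scan.
- **ET scans.** Protocol 5.1.5 calls for an ET visit at permanent discontinuation, with the Week 18 procedures, so including MRI-PDFF. SAP 3.3.6 assigns ET visits to Week 18, and under SAP 3.3.4 the liver fat content (LFC) of a non-completer "will have the value at the ET visit carried forward for the missing Week 18 visit".
- **Interruptions.** Protocol Table 8 orders interruption of study drug for certain liver signals and allows restart under conditions. Neither document says how those days count towards compliance.
- **Pouch counts (Protocol 4.4).** "The number of full and empty study drug pouches will be captured" on the eCRF.
- **Use of the set.** One listed output, Table 14.2.1.3 (LFC by time point).

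**The concern.** A per-protocol analysis is normally read as the result among subjects who received treatment broadly as planned. Here the two conditions that should secure this do not do so. The compliance ratio has a denominator that shrinks with early stopping, and the scan condition accepts an ET scan at any time. Nothing in SAP 4.3 ties membership to the planned 18 weeks.

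The Efficacy Set, which carries the primary analysis, does impose a minimum exposure. The usual order is therefore reversed: the supportive set admits subjects whom the primary set rejects for too little treatment. Table 14.2.1.3 is the SAP's only compliance-restricted view of the primary endpoint. If it differed from the primary result, the reader could not tell whether adherence or short exposure was the reason. If it agreed, that would not be evidence from a stricter population. The disposition summary in SAP 5.1 counts the Safety, Efficacy and Modified Efficacy sets but not this one, so the presence of early stoppers would not show there.

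**Working it through.** **1. The plan's own figure.** Inputs (Protocol 9.2.6, SAP 3.1): difference 5 points, SD 6.3, two-sided 5%, power 90%. Normal approximation: n = 2 × (1.960 + 1.282)² × 6.3² / 5² = 33.4, so 34 per group. With the t distribution, power is 89.7% at 34 and 90.5% at 35, so 35 per group reproduces. Dropout: 35/0.90 = 38.9, so 39 per group and 3 × 39 = 117. The Per Protocol Set plays no part in this.

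**2. Inputs for compliance.** Two pouches a day (SAP 3.2); Week 18 is Day 126 (schedule of events), so the planned course is 126 days and 252 pouches; cut-off 80%.

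Compliance = 100 × (pouches dispensed − pouches returned) / (2 × on-treatment days).

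**3. Early stopping.** A subject who takes every pouch for d days and returns the rest scores 2d/2d = 100% for any d. With dosing on Days 0 to 13, Days on Treatment = 13 − 0 + 1 = 14.

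**4. Interruption, on one reading.** Suppose on-treatment days in SAP 5.1 means Days on Treatment in SAP 3.3.7. A completer over 126 days with a gap of g days, otherwise fully adherent, scores (252 − 2g)/252.

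| Subject | Dosed days | Compliance | Per Protocol Set | Efficacy Set |
|---|---|---|---|---|
| Stops after 14 days, ET MRI within 14 days of last dose | 14 (14/126 = 11.1% of plan) | 28/28 = 100% | In | Out (14 < 80) |
| Completer, 25-day gap | 101 | 202/252 = 80.2% | In | In |
| Completer, 26-day gap | 100 | 200/252 = 79.4% | Out* | In |
| Completer, 46-day gap | 80 | 160/252 = 63.5% | Out* | In |

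*Only on the reading in step 4. If gap days are not on-treatment days, the 26-day case is 200/200 = 100% and stays in.

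The first row alone shows that the Per Protocol Set is not nested in the Efficacy Set.

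**5. Possible dilution.** Neither document gives an early-stop rate. Assume a share p of each arm in the set are early stoppers with no LFC change. The apparent difference is 5 × (1 − p). At the planned dropout rate, p = 0.10, it is 5 × 0.90 = 4.5 points.

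**6. With the fix.** An 80-day minimum removes the 14-day subject. Every remaining member has at least 80 days of dosing and a Week 18 or ET scan, and so belongs to the Efficacy Set. The completer with a 26-day gap passes the 80-day test (100 ≥ 80) but passes the 80% rule only if gap days leave the denominator.

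**The case against.** The best defence is that this set was never meant to be a stricter Efficacy Set. The SAP does not say that it is nested there or that it estimates an 18-week on-treatment effect, and its text admits ET scans openly. It can be read as the Modified Efficacy Set restricted by compliance and by scan timing. Minimum exposure is already handled in the primary set, which itself accepts ET scans from 80 days onward. No analysis in SAP 5.2 names the Per Protocol Set, and only one supportive table uses it.

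Much of this stands: the impact is limited to that table. It does not remove the defect. On this reading, no set in the SAP combines adequate exposure with compliance, and the name invites the reader to assume that this one does.

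A reader might also infer more than the documents support:

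- **That completers with long ordered interruptions are certainly excluded.** SAP 5.1 speaks of on-treatment days without invoking the SAP 3.3.7 definition, and on a plain reading days off drug are not on-treatment days. The exclusion is conditional, needs a gap of at least 26 days with full adherence otherwise, and the documents give no interruption lengths.
- **That unreturned pouches let the wrong subjects in.** Dispensed minus returned does count an unreturned pouch as taken, and there is no upper limit. Someone who stops at 21 days with 42 days' supply and returns nothing scores 42/21 = 200%. If the drug was taken as directed, true compliance is 100% and membership is the same. Protocol 4.2 and 5.1.3 also provide for used and unused pouches to come back at visits.
- **That excluding a completer with 79% intake is an error.** That is simply what an 80% rule does.
- **That the effect could shrink to 4.0 points.** This needs 20% of each arm to be early stoppers, twice the planned dropout.

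**Conclusion.** The point holds for exposure. As written, SAP 4.3 and 5.1 admit a fully adherent 14-day stopper with a prompt ET scan at 100% compliance and 11% of planned treatment, while SAP 4.1 rejects that subject. This follows from the stated rules and needs no assumption beyond the subject's own course. The Per Protocol Set therefore cannot serve as a stricter adherence-based check on the primary result.

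The interruption part is a missing definition with a conditional consequence: compliance of 79.4% or lower, and exclusion, from a 26-day gap upward over 126 days if the SAP 3.3.7 formula applies.

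The size is uncertain but bounded under stated assumptions. With no LFC change in early stoppers, and early stoppers at most 10% of each arm in the set, a 5-point effect would appear as no less than about 4.5 points. Even that floor is demanding: it takes the equivalent of all planned dropouts stopping early, having an ET scan within 14 days, reaching 80% compliance and showing no change. Dropouts without an ET scan never enter.

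A reader might infer that the trial's main conclusion is at risk. It is not: the primary analysis uses the Efficacy Set, and neither it nor the sample size is affected.

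**What to change.** - **SAP 4.3:** add the 80-day dosing minimum already used in SAP 4.1, read in the same way in both places, so that the Per Protocol Set is nested in the Efficacy Set.
- **SAP 5.1, denominator:** define on-treatment days. State that interruption days ordered under the protocol are left out of the compliance denominator where their dates are recorded, and say what is done where they are not. Protocol 4.4 establishes only pouch counts on the eCRF, so the availability of those dates should be checked first.
- **SAP 5.1, numerator:** give a rule for unaccounted pouches, using the full and empty counts on the eCRF. Counting only returned empties would understate intake in subjects who discard them, so the rule should cover pouches returned neither full nor empty.

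The cost is SAP wording, one derived variable and a somewhat smaller Per Protocol Set. The changes should be made before unblinding, since redefining the set afterwards would look data-driven. This concerns only how days and pouches are counted in the analysis; no clinical rule on interruption or restart is proposed.

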4.4. SAFETY SET

The Safety set consists of all subjects who receive at least one dose of study treatment, regardless of whether or not they undergo any study assessments. Subjects in this set will be analyzed according to the treatment which they receive. All safety analyses will be based on this set.

5. STATISTICAL METHODS

Descriptive statistical methods will be used to summarize the data from this study, with hypothesis testing performed for the primary and other selected efficacy endpoints. Unless stated otherwise, the term “descriptive statistics” refers to number of subjects (n), mean, median, standard deviation (SD), minimum and maximum for continuous data and frequencies and percentages for categorical data. Additional statistical methods include analysis of covariance (ANCOVA) and logistic regression. All data collected during the study will be included in data listings. Unless otherwise noted, the data will be sorted first by treatment group, subject number, and then by date within each subject number.

The term ‘treatment group’ refers to all subjects on the same dosing regimen. There will be three treatment groups in this study:

HTD1801 500 mg BID

HTD1801 1000 mg BID

Placebo BID

All statistical tests will be two-sided with an alpha level of 0.05.

The statistical analyses will be conducted with the SAS[®] System version 9.4 or higher. All analyses will be subject to formal verification procedures. Specifically, results will be verified utilizing independent programming prior to issuance of the draft statistical report. All documents will be verified by the lead statistician to ensure accuracy and consistency of analyses.

5.1. SUBJECT DISPOSITION, DEMOGRAPHIC AND BASELINE CHARACTERISTICS

Subject disposition will be presented for all randomized subjects. For each treatment group the following will be presented: the number of subjects who meet all eligibility criteria, the number of

subjects included in the Safety, Efficacy and Modified Efficacy sets, the number of subjects who completed the study and discontinued from the study, and the reasons for early discontinuation at any point. Additionally, the number of subjects dosed will be presented and the number of days on study treatment will be summarized for all treated subjects.

Demographic data and baseline characteristics including age, gender, race, and ethnicity, weight at Baseline, height at Baseline, body mass index (BMI), Baseline LFC, Baseline cT1, Baseline alanine aminotransferase (ALT), Baseline aspartate aminotransferase (AST), Baseline ELF, and Baseline HbA1c will be summarized using descriptive statistics for the Safety population, and will be presented by treatment group. This information will be reviewed for baseline differences, but no statistical testing will be performed.

Data on drug accountability and total amount of study drug received will be summarized by treatment group. Total amount of study drug received will be calculated as the sum over the duration of the study of study drug dispensed – study drug returned. Study drug compliance will then be calculated as this amount divided by the expected amount of drug received based on the number of on-treatment days the subject was on the study x 100.

5.2. EFFICACY ANALYSIS

5.2.1. Primary Efficacy Endpoint

The primary endpoint for this study is the absolute change in LFC as measured by MRI-PDFP from Baseline to Week 18.

5.2.2. Primary Efficacy Analysis

LFC values and change from Baseline will be presented by treatment group and study visit. LS means, standard error, and corresponding 95% confidence intervals for absolute change from Baseline in LFC will be presented by treatment group, and LS mean differences between treatment groups will also be presented with their respective standard errors and confidence intervals. Differences in absolute change from Baseline in LFC will be assessed by analysis of covariance that includes treatment group as a fixed effect, and Baseline LFC and Baseline ALT as covariates. Comparisons of each active treatment group to placebo will be tested at the 5% level of significance without adjustment for multiple tests.

5.2.3. Additional Analyses of the Primary Endpoint

As a secondary analysis, the ANCOVA model from the primary analysis, with the addition of Baseline HbA1c group ($< 7\%$ vs. $\geq 7\%$) as a fixed effect, will be used to obtain a comparison of the two active treatment groups, as well as a comparison of the combined active treatment groups vs. placebo, both tested at the 5% alpha level.

5.2.4. Secondary Efficacy Endpoints

- Change from Baseline and percent change from Baseline in fasting glucose from Baseline to Week 18
- Change from Baseline and percent change from Baseline in HbA1c from Baseline to Week 18.
- Proportion of subjects who achieve $\geq 30\%$ relative reduction in LFC as measured by MRI-PDFP from Baseline to Week 18.
- Percent change from Baseline in LFC as measured by MRI-PDFP from Baseline to Week 18.
- Proportion of subjects who normalize LFC to $< 5\%$ as measured by MRI-PDFP at Week 18.
- Proportion of subjects who achieve $\geq 5\%$ absolute reduction in LFC as measured by MRI-PDFP from Baseline to Week 18.
- Change from Baseline and percent change from Baseline in homeostasis model assessment-estimated insulin resistance (HOMA-IR) from Baseline to Week 18.
- Change from Baseline and percent change from Baseline in low-density lipoprotein cholesterol (LDL-c) from Baseline to Week 18.

- Change from Baseline and percent change from Baseline in serum triglycerides from Baseline to Week 18.
- Change from Baseline and percent change from Baseline in high-density lipoprotein cholesterol (HDL-c) from Baseline to Week 18.
- Changes from Baseline and percent change from Baseline in AST from Baseline to Week 18.
- Changes from Baseline and percent change from Baseline in ALT from Baseline to Week 18.
- Changes from Baseline and percent change from Baseline in GGT from Baseline to Week 18.
- Proportion of subjects with elevated ALT at Baseline who normalize ALT at Week 18.
- Proportion of subjects with elevated AST at Baseline who normalize AST at Week 18.
- Change from Baseline and percent change from Baseline in Pro-C3 from Baseline to Week 18 for subjects with elevated Pro-C3 at Baseline.
- Change from Baseline and percent change from Baseline in the enhanced liver fibrosis (ELF) score and each component of ELF (tissue inhibitor of metalloproteinases 1 [TIMP-1], N-terminal pro-peptide of type III collagen [PIIINP], and hyaluronic acid [HA]) from Baseline to Week 18.
- Change from Baseline and percent change from Baseline in total bile acid from Baseline to Week 18.
- Change from Baseline and percent change from Baseline in total primary bile acids (and metabolites) from Baseline to Week 18.
- Change from Baseline and percent change from Baseline in total secondary bile acids (and metabolites) from Baseline to Week 18.
- Change from Baseline and percent change from Baseline in total ursodeoxycholic acid (and metabolites) from Baseline to Week 18.
- Change from Baseline and percent change from Baseline in 7 α -hydroxy-4-cholesten-3-one (C4) from Baseline to Week 18.
- Change from Baseline and percent change from Baseline in fibroblast growth factor 19 (FGF19) from Baseline to Week 18.

5.2.5. Secondary Efficacy Analysis

Change and percent change from Baseline in LFC will be summarized by treatment group and study visit. Differences in percent change from Baseline in LFC will be assessed by analysis of covariance that includes the effects of treatment group, Baseline LFC, and Baseline ALT, comparing each active treatment group to placebo, as well as a comparison of the combined active treatment groups vs. placebo. A figure summarizing LS means of percent change from Baseline at Week 18 by treatment group will also be generated.

Changes from Baseline to Week 18 in the laboratory assessments listed as secondary efficacy endpoints (fasting glucose, HbA1c, HOMA-IR, LDL-c, serum triglycerides, HDL-c, AST, ALT,

Pro-C3, ELF, total bile acids, C4, FGF19) will be assessed by analysis of covariance that includes the effects of treatment group and Baseline value, comparing each active treatment group to placebo. For these analyses, missing Week 18 values will be imputed using the methods described in section 3.3.4. For HbA1c, this model will also be run without imputed values. For all bile acid analyses other than total bile acid, all analyses will be performed without imputation. Figures summarizing change from Baseline over time by treatment group will also be generated for these laboratory assessments. The number and percentage of subjects who achieve $\geq 30\%$ relative reduction in LFC as measured by MRI-PDFF from Baseline to Week 18 will be summarized by treatment group and study visit. The proportion of subjects who achieve $\geq 30\%$ relative reduction in LFC as measured by MRI-PDFF from Baseline to Week 18 will be analyzed by logistic regression that includes the effects of treatment group, Baseline LFC, and Baseline ALT. A figure summarizing the proportion of subjects achieving $\geq 30\%$ relative reduction in LFC as measured by MRI-PDFF from Baseline to Week 18 by treatment group will also be generated.

The number and percentage of subjects who normalize LFC to $< 5\%$ as measured by MRI-PDFF at Week 18 will be summarized by treatment group and study visit. The proportion of subjects who normalize LFC to $< 5\%$ as measured by MRI-PDFF at Week 18 will be analyzed by logistic regression that includes the effects of treatment group, Baseline LFC, and Baseline ALT. A figure summarizing the proportion of subjects who normalize LFC to $< 5\%$ at Week 18 by treatment group will also be generated.

The number and percentage of subjects who achieve $\geq 5\%$ absolute reduction in LFC as measured by MRI-PDFF from Baseline to Week 18 will be summarized by treatment group and study visit. The proportion of subjects who achieve $\geq 5\%$ absolute reduction in LFC as measured by MRI-PDFF from Baseline to Week 18 will be analyzed by logistic regression that includes the effects of treatment group, Baseline LFC, and Baseline ALT. A figure summarizing the proportion of subjects who achieve $\geq 5\%$ absolute reduction in LFC from Baseline to Week 18 by treatment group will also be generated.

The number and percentage of subjects with elevated ALT at Baseline who normalize ALT at Week 18 will be summarized by treatment group and study visit. The proportion subjects of with elevated ALT at Baseline who normalize ALT at Week 18 will be analyzed by logistic regression that includes the effects of treatment group, Baseline LFC, and Baseline ALT. A figure summarizing the proportion of subjects who normalize ALT at Week 18 by treatment group will also be generated. For this analysis, missing Week 18 values will be imputed using the multiple imputation method as described in section 3.3.4.

If the data is not amenable to analysis by logistic regression for any of the responder endpoints included in this section, then comparisons between treatment groups may be performed using Cochran-Mantel Haenszel (CMH) testing instead.

